10.1 Volume of blood sampling

Each individual blood sample volume is detailed below. The volumes for individual samples may vary accordingly to local laboratory requirements, however the total volume is not expected to exceed 500 mL per subject.

| | |
|---|--------|
| Biochemistry/ hematology | 6 mL |
| LH | 3.5 mL |
| FSH | 4 mL |
| PK | 6 mL |
| Estradiol, testosterone, ACTH, cortisol, TSH, T3 and T4 | 4 mL |

10.2 Efficacy assessments

10.2.1 Hot flash paper-diaries

Subjects will document the number of individual hot flashes experienced and rate the severity of each on a scale of 1 to 3 (mild, moderate or severe). The diaries are to be completed twice daily, in the morning and evening. The diaries are to be completed for the 2 weeks prior to Baseline visit to ascertain eligibility and from Screening until the morning of Day 15 (the last entry being the information from overnight). Subjects will also record the number of times that they were awake through the night (night time awakening [NTA]), secondary to hot flashing.

10.2.2 Day time continuous hot flash diary

Whilst in the clinic on Days -1, 1 through 7 and Day 14, subjects will record each hot flash and severity (scale of 1 to 3) in the hot flash paper-diary as they occur during the day and night. Subjects will also be required to push a button on the skin conductance monitor (see Section 10.2.3) when they sense a hot flash and then record the event in the diary. For Day -1 and Day 14 subjects will be provided with the continuous diary at the previous visit and instructed to start completing it upon waking in the morning on Day -1 and Day 14 prior to admission to the unit.

10.2.3 Sternal skin conductance monitors

Studies have shown that rather than over-reporting hot flashes when they do not occur, women tend to under report them when asked to complete hot flash diaries, thus leading to inaccuracy. Objective assessment is therefore useful and can be achieved using a sternal skin conductance monitor [Bahr et al., 2014]. Sternal skin conductance monitors will be fitted on Day -1 (24 hours \pm 1 hour prior to the planned study drug administration on Day 1) and will remain in place until after the Day 7, 24 hour assessments are completed (Day 8).

The sternal skin conductance monitors will be refitted around 30 minutes prior to study drug administration on Day 14 and remain in place until after the 24 hour assessments are completed on Day 15.

Subjects will be required to push a button on the skin conductance monitor when they sense a hot flash when fitted with the monitor and then provide details of the hot flash in the continuous hot flash diary.

10.2.4 Luteinizing hormone

Blood samples for analysis of LH will be collected every 60 minutes from time 0 (pre-dose) to 8 hours on Day 1 and Day 7. The same sampling schedule will also be followed on Day -1, starting at a similar time to that planned for Days 1 and 7.

LH samples will be collected as close to the nominal time point as possible. The allowable window for LH sample collection relative to dosing will be ± 5 minutes.

10.3 Pharmacokinetics

Blood samples for PK analysis will be collected at the following time points on Day 1 and Day 7:

Pre-dose; 0.5; 1.0; 1.5; 2.0; 2.5; 3.0; 4.0; 5.0; 6.0; 8.0; 12.0; 24.0 hours

On Day 14 blood samples will be taken for PK analysis at the following time points:

Pre-dose; 0.5; 1.0; 1.5; 2.0; 2.5; 3.0; 4.0; 5.0; 6.0; 8.0; 12.0; 24.0, 48.0, 72.0 hours

The pre-dose sample will be collected within 30 minutes prior to dose administration. On Days 1 and 7 the 24 hour PK sample must be taken prior to the dose of study medication the following morning.

Blood samples may be collected via a cannula or by direct venipuncture.

Pharmacokinetic samples will be collected as close to the nominal time point as possible. Allowable windows for PK sample collection relative to dosing (the dose at the start of the PK profile) will be as follows: ± 2 minutes up to and including 2 hours post-dose, ± 5 minutes up to and including 8 hours post-dose, ± 10 minutes up to and including 24 hours post-dose; ± 30 minutes up to and including 72 hours post-dose.

The visits on Days 16 and 17 must be scheduled to enable the samples to be taken at 48 and 72 hours, ± 30 minutes, relative to the final dose on Day 14.

10.3.1 Sample transfer and assay methodology

Plasma analysis will be performed under the management of Aptuit, SRL, Italy. Concentrations of NT-814 will be determined in plasma using the current Sponsor-approved analytical methodology. Raw data will be stored in the Good Laboratory Practice Archive of Aptuit. Please refer to the laboratory manual for further details.

Plasma concentration data will be transferred to Parexel International, USA, who will be responsible for generating the relevant tables and listings, and performing the PK analysis as described in Section 11.3.3.

10.4 Safety assessments

10.4.1 Medical history and concomitant diseases

The investigator must record all medically and clinical relevant information regardless of the time since the date of diagnosis.

History should include (but is not limited to):

- All current and past medications taken during 3 months before the Screening Visit
- Relevant history of respiratory, cardiovascular, renal, gastro-intestinal, hepatic, endocrine, hematological, neurological, psychiatric and any other diseases

10.4.2 Physical examinations

A full physical examination will be conducted at the time points indicated in the Study Schedule in [Table 2](#). This will be completed by a physician or an appropriate qualified delegate.

A full physical examination is composed of a review of the following body systems:

- General appearance
- Skin
- Head, eyes, ears, nose and throat
- Respiratory
- Cardiovascular
- Abdomen (including liver and kidneys)
- Musculoskeletal
- Neurological

Any abnormalities that are identified at the Screening Visit will be documented on the medical history eCRF page. Any changes (including new and worsening findings) between the Screening Visit and final study visit should be captured as AEs on the AE eCRF page, as determined by the Investigator and documented in the subject's notes.

If an improvement/resolution of a physical examination finding documented in the subject's medical history occurs during the study, it should be recorded in the source document. If there is resolution of a physical examination finding previously noted as an AE, then the event resolution and stop date should be recorded on the AE eCRF page and documented in the subject's notes.

10.4.3 24-hour Holter monitoring

Subjects will be fitted with Holter monitors upon admission to the Phase 1 unit on Day -1. These will remain in place until after the 24-hour assessments are completed on Day 7 (Day 8). Subjects will be fitted with Holter monitors again upon admission to the clinic on Day 14. These will remain in place until after the 24-hour assessments are completed on Day 14 (Day 15).

10.4.4 12-lead ECGs

12-lead ECG data captured by the Holter monitors will be collected at the timepoints indicated in the Study Schedule in [Table 2](#).

On Days 1 and 14, resting 12-lead ECG data will be collected at the following timepoints: pre-dose and at 0.5, 1.0, 1.5, 2.0, 2.5, 3.0, 4.0, 8.0, 12.0 and 24.0 hours (all +/- 15 mins).

The same assessment schedule is also required on Day -1, starting at a similar time to that planned for Days 1 and 14. On Day 1 the 24 hour ECG must be performed prior to the dose of study medication the following morning.

Once daily ECG recordings will be made just prior to dosing (approx. 30 mins) on all other days during the inpatient stay (Days 3 to 8).

These specific 12-lead ECG recordings should be collected in accordance with the priority order of study assessments detailed in [Section 10.5](#).

10.4.5 Biochemistry

Blood for biochemistry assessments will be collected as indicated in the Study Schedule ([Table 2](#)). The following clinical chemistry/ biochemistry parameters will be assessed: sodium, potassium, glucose, urea, creatinine, creatine kinase, albumin, calcium, phosphate, bilirubin (total), alkaline phosphatase, AST, ALT, gamma-glutamyl transferase (GGT), bicarbonate, magnesium, chloride, total protein, total cholesterol, low-density lipoprotein (LDL), high-density lipoprotein (HDL), triglycerides.

10.4.6 Hematology

Blood for hematology assessments will be collected as indicated in the Study Schedule ([Table 2](#)). The following hematology parameters will be assessed: RBC, WBC, hematocrit, hemoglobin, MCV, platelets, WBC differentials, prothrombin time, activated partial thromboplastin time (APTT).

10.4.7 Urinalysis

Urinalysis assessments will be conducted as indicated in the Study Schedules ([Table 2](#)). Urinalysis will include glucose, bilirubin, ketones, specific gravity, blood, pH, protein, urobilinogen, nitrites, leucocytes, sedimentation.

10.4.8 Hormone level assessments

Blood samples will be collected to assess estradiol, testosterone, FSH, ACTH, cortisol, TSH, T3 and T4 when the subjects are admitted to the unit on Day -1 and again prior to discharge on Day 15.

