8.2 Safety endpoints

Safety and tolerability will be assessed by the following:

- Physical Examinations
- Analysis for arrhythmias as assessed by continuous Holter monitoring from Day -1 to Day 8 (24 hours post Day 7 dose) and Day 14 (24 hours)
- Abnormalities on the 12-lead ECGs
- Change in ECG variables (heart rate, RR, PR, QRS, QT, QTcF and QTcB)
- Change from Baseline in clinical laboratory assessments including lipids and coagulation profile
- Change from baseline in hormones including estradiol, testosterone, follicle stimulating hormone (FSH), adrenocorticotropic hormone (ACTH), cortisol, thyroid-stimulating hormone (TSH), triiodothyronine (T3) and thyroxine (T4)
- Change from Baseline in vital signs including oxygen saturation, oral temperature and postural blood pressure (BP) changes
- Adverse events (AEs) of dehydration (supported by changes in serum urea and creatinine, urinary sediment and weight and vital signs)
- Nature and severity of Adverse Events (AE)
- Withdrawals due to AEs

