9.8 Discontinuation criteria

Subjects meeting any of the following criteria (regardless of treatment assignment) will be required to stop study medication and complete the early termination visit assessments:

- Intolerable complaints of undesirable sexual side effects from the study medication
- Oxygen saturation < 90% during a laboratory session that does not increase after administration of supplemental oxygen.
- If AST and ALT increase to ≥ 3 times the upper limit of normal
- Clinically relevant cardiovascular AE such as ventricular tachycardia or atrial fibrillation

- Signs of dehydration (e.g. orthostatic hypotension or decreasing urine outflow, impaired renal function or biochemistry profile change from the baseline, weight loss more than 10% from the baseline)

Subjects that discontinue early may be replaced.

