10. STUDY SCHEDULE

Table 2: Schedule of Events

| Procedure | Visit 1 Screen | Visit 2 | | | | Visit 3 | | Outpatient visits | | Early term visit ¹² | Follow-up Phone call ¹¹ |
|---|-------------------|----------------|----------------|-------|-------|----------------|--------|-------------------|--------|--------------------------------------|---------------------------------------|
| | | Day -1 | Day 1 | Day 7 | Day 8 | Day 14 | Day 15 | Day 16 | Day 17 | | Day 21 |
| Informed Consent ¹ | X | | | | | | | | | | |
| Medical History/ Concomitant Diseases | X | X | | | | | | | | | |
| Physical Examination | X | | X | | X | | X | | | X | |
| Inclusion/Exclusion criteria | X | X | X ² | | | | | | | | |
| Outpatient visit | X | | | | | | | X | X | X | |
| Admission | | X | | | | X | | | | | |
| Inpatient stay | | ←————→ | | | | ←————→ | | | | | |
| Discharge | | | | | X | | X | | | | |
| Randomization | | | X | | | | | | | | |
| Vital signs ³ | X | X | X | X | X | X | X | | | X | |
| 12-lead ECG | X | X ⁴ | X ⁴ | X | X | X ⁴ | | | | | |
| Hot flash paper diary ⁵ | X | X | X | X | X | X | X | | | | |
| Day time continuous hot flash paper diary ⁵ | | X | X | X | | X | | | | | |
| Sternal Skin conductance monitor ⁶ | | X | X | X | | X | | | | | |
| Holter monitor ⁶ | | X | X | X | X | X | X | | | | |
| AE/SAE recording | X | X | X | X | X | X | X | X | X | X | X |
| Dose medication ⁷ | | | ←————→ | | | | | | | | |
| Medication Dispensed ⁷ | | | | | X | | | | | | |
| Biochemistry/ Hematology | X | X | | | X | X | | | | X | |
| Urinalysis | | X | | | X | X | | | | X | |
| LH ^{8, 10} | | X | X | X | | | | | | | |
| estradiol, testosterone, FSH, ACTH, cortisol, TSH, T3 and T4 | | X | | | | | X | | | | |
| PK ^{9, 10} | | | X | X | | X | | X | X | | |

Key:

- 1 Informed consent must be signed by the subject before the start of any study procedure
- 2 Baseline assessments to be conducted on Day 1, prior to dosing. Key inclusion/exclusion criteria must be re-assessed before conducting any other baseline assessments
- 3 Vital signs include sitting and standing BP, heart rate, oral body temperature, pulse oximetry, respiration rate and weight will be performed daily during inpatient stays. Vital sign assessments will be performed on Day -1 at a similar time to the same assessments that are planned pre-dose on Day 1. The assessments will then be performed just prior to dosing (approx. 30 mins) for all other days in clinic and at a similar time on Day 15.

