4.10.2 Clinical Laboratory Assessments

Clinical chemistry/ biochemistry and hematology sampling will be performed at screening and on Days -1, 8, 14, and early termination. The following clinical chemistry/ biochemistry parameters will be assessed: sodium, potassium, glucose, urea, creatinine, creatine kinase, albumin, calcium, phosphate, bilirubin (total), alkaline phosphatase, aspartate aminotransferase, alanine aminotransferase, gamma-glutamyl transferase, bicarbonate, magnesium, chloride, total protein, total cholesterol, low-density lipoprotein, high-density lipoprotein, triglycerides. The following hematology parameters will be assessed: red blood cells, white blood cells, hematocrit, hemoglobin, mean corpuscular volume, platelets, white blood cell differentials, prothrombin time, and activated partial thromboplastin time.

Urinalysis sampling will be performed on Days -1, 8, and 14. Urinalysis will include glucose, bilirubin, ketones, specific gravity, blood, pH, protein, urobilinogen, nitrites, leucocytes, and sedimentation.

Blood samples will be collected to assess estradiol, testosterone, FSH, ACTH, cortisol, TSH, T3, and T4 when the subjects are admitted to the unit on Day -1 and again prior to discharge on Day 15.

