8.11 Analysis of Safety Data

8.11.1 General

All analyses will be performed using the safety set.

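### The hormone panel is not drawn at the early termination visit, so a woman who stops before Day 15 has no scheduled post-dose value for this safety endpoint

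*Protocol*

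**What the plan says.** The primary objective (Protocol 6.1) covers the PK and safety profile of NT-814 against placebo. Protocol 8.2 and SAP 3.4 include hormone change from baseline among the safety endpoints. Protocol 11 states that there is no primary hypothesis test.

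Protocol 10.4.8 has the panel drawn "when the subjects are admitted to the unit on Day -1 and again prior to discharge on Day 15". The hormones are "estradiol, testosterone, FSH, ACTH, cortisol, TSH, T3 and T4". SAP 4.10.2 opens its sentence with "Blood samples will be collected to assess estradiol, testosterone, FSH, ACTH, cortisol, TSH, T3, and T4" and gives the same two days.

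Protocol 9.8 sends a woman who meets a discontinuation criterion to the early termination visit. The first criterion is "Intolerable complaints of undesirable sexual side effects from the study medication". Under Protocol 9.9, if a stopping rule is met during a cohort, the women then on treatment are asked to stop dosing and, where possible, to have the same visit.

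For the analysis, SAP 8.11.1 says "All analyses will be performed using the safety set", which means all dosed women. SAP 8.11.3 summarizes hormone values and changes by treatment at each time point. SAP 8.1 lists unscheduled and repeat results but leaves them out of the safety summaries. SAP 8.2 bases summaries primarily on non-missing values. Neither document has a rule for a missing hormone value.

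**The concern.** There is one post-dose hormone sample, and it falls after the last dose. A woman who stops earlier, for whatever reason, contributes a baseline and nothing else to this endpoint. She still attends a visit at which blood is taken.

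Two things are at stake. The first is individual safety information: a woman withdrawn for an adverse event leaves without a scheduled hormone measurement. Protocol 5.4 reports only one woman previously exposed to NT-814, so female hormone data before this study are close to nil. The second is the summary itself. It is headed Safety Set, but its post-dose rows can hold only women who reached Day 15. If their hormone change differs from that of women who stopped, the summary does not describe all dosed women.

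The gap would be widest where it matters most. If a stopping rule were met mid-cohort, every woman then on treatment would lack a scheduled post-dose hormone value at the dose that triggered the stop.

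**Working it through.** **Is the gap real?** The two relevant rows of Protocol Table 2 can be set side by side. The columns run: Screening, Day -1, Day 1, Day 7, Day 8, Day 14, Day 15, Day 16, Day 17, early termination, follow-up.

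- Hormones: "estradiol, testosterone, FSH, ACTH, cortisol, TSH, T3 and T4 | | X | | | | | X". The marks fall on Day -1 and Day 15, and the early termination cell is empty.
- Biochemistry and hematology: "Biochemistry/ Hematology | X | X | | | X | X | | | | X". The last mark falls in the early termination column.

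Physical examination, vital signs and urinalysis are also marked at early termination, so the column is in use and the blank belongs to the hormone row. Protocol 10.4.8 and SAP 4.10.2 confirm it in words, so it is not a table-reading artefact. Nothing else fills it: the biochemistry list in Protocol 10.4.5 contains no hormones, and LH (Protocol 10.2.4) is a separate exploratory measure taken on Days -1, 1 and 7.

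Scheduled post-dose hormone samples per woman are therefore 1 if she reaches Day 15 and 0 if she stops earlier.

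**How large could the effect on the mean be?** The plan gives no dropout rate, hormone effect or related figure to reproduce, so what follows rests on assumptions.

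Inputs: 15 NT-814 women per cohort (Protocol 11.1); k women who stop before Day 15 (assumed 1, 2 or 3); r, the ratio of the stoppers' mean change to that of women who reach Day 15 (assumed 2, 1 or 0.5).

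Set the mean change in women who reach Day 15 to 1. The all-dosed mean is ((15 − k) + k·r)/15, and the relative error of the Day 15 mean is 15/((15 − k) + k·r) − 1.

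| k | r = 2 | r = 1 | r = 0.5 |
|---|---|---|---|
| 1 | 15/16 − 1 = −6% | 0% | 15/14.5 − 1 = +3% |
| 2 | 15/17 − 1 = −12% | 0% | 15/14 − 1 = +7% |
| 3 | 15/18 − 1 = −17% | 0% | 15/13.5 − 1 = +11% |

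Negative means that the Day 15 mean understates the all-dosed mean. Put another way, the absolute bias is (k/15) times the difference between the groups: 0.07, 0.13 or 0.20 SD for each 1 SD of difference.

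The table assumes no replacement. Protocol 7.4 allows it, but it restores the count at Day 15 without supplying the stoppers' values. With k = 3 replaced and r = 2, the all-dosed mean is (15 + 3·2)/18 = 21/18, and the error is 18/21 − 1 = −14%.

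**How likely is at least one missing value in an arm of 15?** With an assumed stopping probability p, the chance is 1 − (1 − p)^15: 26% at p = 0.02, 54% at 0.05, 79% at 0.10 and 96% at 0.20.

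**Is there room for the blood?** Using the volumes in Protocol 10.1, a woman who completes the schedule gives:

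- PK: (13 + 13 + 15) × 6 mL = 246 mL
- LH: 3 days × 9 samples × 3.5 mL = 94.5 mL
- Biochemistry/hematology: 4 × 6 mL = 24 mL
- Hormones: 2 × (4 + 4) mL = 16 mL

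The total is 380.5 mL against the 500 mL limit. Even with an early termination draw of 6 + 8 mL on top, it is 394.5 mL.

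**The case against.** The strongest reply is that this is a small, descriptive Phase 1b endpoint. Hormones are one of several listed safety measures, no hypothesis is tested on them, and no stopping criterion in Protocol 9.9 names the panel. Dosing lasts 14 days and more than half of it is inpatient, so few women may stop. A by-visit summary of the Safety Set using observed values is ordinary practice: a woman who stops on Day 5 is also absent from the Day 14 biochemistry row. All of this stands, and it limits the weight of the point. In particular, there is no contradiction in the use of the Safety Set.

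A reader might also infer that the women missing at Day 15 are those with the largest hormonal effects, so that the change at a poorly tolerated dose is understated. The sexual side effect criterion in Protocol 9.8, and the use of testosterone as a target-engagement marker in Protocol 9.2, make that tempting. The documents do not support it. Only one of the five criteria in 9.8 is sexual, and the documents tie none of the five to these hormones. The testosterone model came from Phase 1 studies in 89 men and one woman. Stoppers have also taken fewer doses, so their measured change could equally be smaller.

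Nor does the plan leave a stopper's hormone status certain to go unrecorded. Protocol 10.6 requires follow-up of adverse events ongoing at exit, a clinic visit may replace the follow-up call, and SAP 8.1 would list any unscheduled result. Protocol 10.7 lets the Safety Review Committee add sampling for later cohorts. None of these provisions requires a hormone draw, however, and none puts a stopper's value into a summary.

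**Conclusion.** The gap holds as a matter of scheduling. No post-dose hormone sample is planned for a woman who stops before Day 15, and the resulting summary describes only those who get that far.

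The direction and size of any bias are unknown. Over the assumed range it runs from a 17% understatement to an 11% overstatement of the all-dosed mean, and it is nil if stoppers and the rest change alike. These figures depend wholly on the assumed 1 to 3 stoppers in 15 and the assumed ratios of 0.5 to 2. They do not cover a mid-cohort stop, where a whole group could be missing.

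It would go too far to call hormones a primary safety endpoint: the protocol lists them as a safety endpoint under a broad primary objective. The point is worth acting on because the missing data fall partly on women stopped for safety reasons and the remedy is cheap. It is not a reason to doubt the trial's main results.

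**What to change.** Add the hormone panel to the early termination column of Protocol Table 2, to Protocol 10.4.8 and to SAP 4.10.2, drawn with the biochemistry sample already taken at that visit.

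In SAP 8.11.3 and Tables 14.3.5.2 and 14.3.5.4, add a row for end of treatment, defined as Day 15 or early termination, for the Safety Set. Keep the Day 15 row unchanged beside it. The SAP needs to name this row explicitly, because it otherwise summarizes by scheduled time point and gives no rule for early termination hormone values.

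The cost is about 8 mL of blood (4 mL for FSH and 4 mL for the other hormones) and one row in each of two tables, with no extra visit. The downside is that early termination samples will vary in days on drug, time since the last dose and time of day. The added row is therefore supportive, and its main value is safety follow-up of individual women.

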10.4.9 Vital signs

Vital signs will be measured at the time points indicated in the Study Schedule (Table 2) and will include sitting and standing BP, heart rate, pulse oximetry, oral body temperature, respiration rate and weight.

